injection of Exparel can provide adequate pain relief over 3 days it can make obsolete the need to place a continuous nerve block catheter. There are significant benefits to this. It requires more skill and time to place a catheter versus a single injection of a local anesthetic for a TAP block. Other benefits are related to the avoidance of catheter maintenance including dressings, leakage at catheter insertion site, and the need for additional infusion pumps. Furthermore, any catheter has the possibility of infection or bleeding.

It is the purpose of this study to evaluate the efficacy of methods that allow for continuous release of local anesthetic in the TAP space, either via catheter or via injecting Exparel® a slow release liposomal space versus the standard single injection Bupivacaine in the TAP space. The study shall consist of three (3) arms of which patients will be randomly assigned: Continuous TAP block (CTAP) via Catheter, Single Injection TAP block with the slow release liposomal Exparel, and Single Injection TAP block with Bupivacaine. Several parameters will be measured with the primary goal being to determine the effectiveness and duration of post-operative pain relief.^{8,9}

Primary Hypothesis

Methods that allow for continuous release of local anesthetic in the TAP space will decrease total narcotic requirements vs. the standard single shot Bupivacaine control. A continuous release of local anesthetic in the TAP space via catheters over 2 days will result in lower total narcotic requirements when compared to the single shot Bupivacaine injection technique when measured over 48 hrs. The Liposomal agent Exparel® which releases the Bupivacaine local anesthetic over three days should also allow for a single injection technique that can provide similar post-operative pain response to that of the catheter method without the need to place a catheter in the TAP space. Post-operative narcotic requirements are inversely related to post-operative pain control and patient satisfaction and total narcotic requirements will be significantly higher in the single shot group vs. the continuous release groups over 48 hrs.

Purpose of the Study Protocol

The purpose of this study protocol is to ensure consistent implementation of this study across all study sites.

B Background

Prior Literature and Studies

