Although, there is a fair amount of literature and case reports for TAP block for post-op pain; there is very little data that goes out as far as 72 hrs. Furthermore, those studies (albeit limited) demonstrate a difference that is not considered statistically significant between single shot TAP block and controls that did not receive TAP block at 72 hrs. Studies do however show a statistically significant difference in narcotic requirements and pain scores at 24 hrs (post-operative day [POD] #1), and at 48hrs (POD #2) between single shot TAP and placebo^{4,12} and also between continuous TAP techniques and placebo¹³. However, no direct comparison study exists between continuous TAP Block techniques and standard single shot Bupivacaine technique. Using prior studies as a reference and making the appropriate equianalgesic conversions to account for the difference in narcotic potencies used in the various studies we can come to the expectation that total hydromorphone (Dilaudid) requirements would be roughly 50% lower in the continuous catheter TAP technique vs. the standard single shot Bupivacaine TAP technique at 48hrs. We estimate total Hydromorphone requirements over 48 hrs. in the control (single shot TAP) to be equal to 4.1mg versus the continuous catheter TAP group equaling 2.4 mg. We would also assume Exparel TAP to be equal to catheter TAP at 2.4 mg. Furthermore, Visual Analog Scales as expected follow a similar trend, with the most significant difference seen at 48 hrs.^{4,11-13}

Rationale for this Study

The rationale for this study is to examine the post-operative pain benefits of continuous release TAP techniques (Catheter technique and liposomal slow release Exparel® technique) versus the

standard single shot Bupivacaine injection for TAP block. Therefore, in this study the standard single shot Bupivacaine technique acts as the control.

Although both modalities of continuous release TAP block have been proven versus placebo to provide post-operative pain relief over an extended time period; there is no such study that directly compares the standard single shot Bupivacaine technique to the continuous release TAP techniques in terms of quality or ability to control post-operative pain. Given the significant increased cost along with in the case of the catheter group skill, procedural time, and maintenance management there should be a significant improvement in post-operative pain duration versus the single shot Bupivacaine TAP block technique.

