F3.d Data Collection Procedures for Adverse Events

Please see Attachment L2 for data collection form. All adverse event data will be entered into Oncore ERM.

F3.e Reporting Procedures

Serious Adverse Events and adverse events that meet "severe" criteria must be directly reported within 24 hours to the Principal Investigator, and the IRB.

[name] M.D.
[contact]
[contact]
Department of Anesthesiology
Midwestern Regional Medical Center
Zion, IL

Other adverse events must be entered within 7 days of collection into the Oncore ERM.

F3.f Post-study Adverse Event

Serious Adverse Events and adverse events that meet "severe" criteria must be directly reported within 24 hours to, the Principal Investigator and the IRB.

[name] M.D.
[contact]

[contact]
Department of Anesthesiology
Midwestern Regional Medical Center
Zion, IL

Other adverse events must be entered within 7 days of collection into the Oncore ERM.

F3 Study Outcome Measurements and Ascertainment

G Statistical Plan

Interim Monitoring and Early Stopping

The Principal Investigator will utilize the Oncore ERM study management system to monitor the study.

The study may be stopped early for the following reasons:

- withdrawal of funding
- safety issues
- drug has been proven effective and no further testing is needed

Analysis Plan

The study is a prospective, randomized, open, active controlled clinical trial. Effectiveness of the Continuous TAP (CTAP) via the ON-Q[®] Pain Management System will be evaluated and compared to single shot techniques with respect to reductions in postoperative opioid consumption over the first 72 hours postoperatively. Secondary outcomes including hospital length of stay (LOS), time in PACU, pain at rest and with activity, return of bowel function, and incidence of opioid related side effects will also be evaluated.

The aims of this study are to compare the efficacy of continuous TAP block via ON-Q[®] system versus that of single injection techniques for TAP block regarding opioid reduction among patients undergoing major abdominal surgery. It is hypothesized that a continuous TAP block technique reduces pain, the need for opioids as well as the expected length of stay relative to those resulting from those subjects receiving a single TAP injection of Exparel (liposomal Bupivacaine) or single TAP injection of Ropivacaine to treat postoperative pain.

Study success criteria:

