Based on the above hypothesis this study will be considered successful in demonstrating superior efficacy relative to control if consumption of opioids postoperative is significantly less among patients randomized to receive a

continuous TAP block via the ON-Q[®] system compared to the patients randomized to receive a single TAP injection of Exparel (liposomal bupivacaine) or single TAP injection of Ropivacaine to treat postoperative pain. However, a finding of no difference between the continuous catheter technique and the Exparel arm would also be considered beneficial to the advancement of post-operative pain control techniques because it would demonstrate similar post-operative pain control can be achieved without the extra time and skill required to place a catheter.

Statistical Methods

Sample Size

The main objective of study is to compare total opioid consumption between the single shot TAP group and the Exparel TAP group with a parallel design. Based on previous studies and internal pilots, the mean total opioid consumption (standard deviation) was 4.1 mg (SD 3 mg) in single shot group and 2.4 mg (SD 1.3 mg) in Exparel TAP group. For the sample size calculation, a standard deviation of 3 is used as a conservative estimate. To detect a difference in mean opioid consumption between treatment groups, 4.1 mg vs. 2.4 mg, a sample size of 49 patients per arm is required to achieve 80% power with a significance level of 0.05 using a two-sided t-test or Wilcoxon rank-sum test depending on normality test. A secondary aim is to examine a difference in mean opioid consumption between the single shot TAP group and continuous TAP group. Allowing for a 10% dropout rate, a total of 159 participants with 53 participants in each arm will therefore need to be recruited into the study. It anticipated that approximately 8 participants per week will be enrolled into this study, thus the estimated accrual time is around 1 year.

Statistical Analysis Plan

All analyses will be conducted on patients following an intention-to-treat principle, including all randomized participants enrolled in three arms, in case of relevant non-compliance to the treatment and/or impossibility to evaluate the endpoints, a per-protocol analysis will also be performed, together with an analysis of non-compliance/non-evaluation.

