Patient characteristics and outcomes data will be summarized by cross-tabulation (categorical variables), quartiles (median, ordinal variables), and mean and standard deviation (continuous variables). Comparisons between groups will use Chi-square test or Fisher's exact test as appropriate for categorical variables and t-test or Wilcoxon rank-sum test as appropriate for continuous variables.

Analyses of primary outcome will examine differences in mean opioid consumption between the single shot TAP group and the Exparel TAP group. Analyses of secondary outcomes will examine differences in mean opioid consumption between the single shot TAP group and continuous TAP group. Treatment groups will be compared using a

student's t-test if data are normal distributed or Wilcoxon rank-sum test if not normal distributed.

The differences in mean opioid consumption across three groups (single shot TAP, continuous TAP, and Exparel TAP) will be examined with a test of means between groups using one-way analysis of variance (ANOVA). A comparison between continuous TAP and Exparel TAP will be performed. A t-test will be used if the observations in each trial arm are normally distributed; if non-normally distributed, then rank-based methods such as Wilcoxon rank-sum test will be employed.

All tests will be two-sided.

The overall incidence of serious adverse events and adverse events and number and proportion of patients reporting such events will be summarized by treatment group. Adverse events will be tabulated and summarized by the number and percentage of subjects who experienced the event.

Missing Outcome Data

Analysis will be conducted as described in prior section. Missing data will not be included in the analysis; however, may lead to an increase in patients recruited into one or more study arms.

Unblinding Procedures

This study is not blinded because it will be obvious to all care givers whether or not the patient received a continuous block with catheters or not.

H Data Handling and Record Keeping

Confidentiality and Security

Data will be collected on the data collection forms located in Attachment L9 and entered into the Oncore ERM study management system.

Data collection forms will be stored at each respective study site within a locked cabinet in a locked research office.

The Oncore ERM study management system is a secure web-based management system that is password-protected. Access to data is role-specific.

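### A non-significant catheter versus Exparel test would be read as proof of similar pain control, but only tests of difference are planned for that pair

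*Combined protocol and SAP*

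**What the plan says.** Study success criteria (section G) defines success as significantly lower opioid use with the catheter, "compared to the patients randomized to receive a single TAP injection of Exparel" or the other single injection. It then adds that "a finding of no difference between the continuous catheter technique and the Exparel arm would also be considered beneficial", and gives as the reason "because it would demonstrate similar post-operative pain control can be achieved without the extra time and skill required to place a catheter".

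For this pair, the Statistical Analysis Plan says "A comparison between continuous TAP and Exparel TAP will be performed". The method is a t-test, and "if non-normally distributed, then rank-based methods such as Wilcoxon rank-sum test will be employed". A one-way ANOVA across the three arms is also planned, and all tests are two-sided. The Sample Size section powers single shot versus Exparel only.

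The documents expect different things of this pair:

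- The Primary Hypothesis says Exparel "can provide similar post-operative pain response to that of the catheter method without the need to place a catheter".
- Prior Literature and Studies (section B) says "We would also assume Exparel TAP to be equal to catheter TAP at 2.4 mg".
- The Analysis Plan (section G) hypothesizes that the catheter reduces pain, opioid need and length of stay "relative to those resulting from those subjects receiving a single TAP injection of Exparel".

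**The concern.** The t-test, the Wilcoxon test and the ANOVA all take no difference as the null hypothesis. Failing to reject that null can mean that the arms are alike, or that the data are too few or too variable to tell them apart. Under the sentence as written, fewer patients or noisier data make the similarity conclusion easier to reach. A claim of similarity needs a margin fixed in advance and a confidence interval judged against it, and the plan has neither.

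The conflicting expectations add to the problem. A significant result in favour of the catheter counts as success, and a non-significant one counts as a demonstration of similarity, so both support a favourable conclusion. What is at stake is the practical message that one injection can replace a catheter.

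**Working it through.** **Inputs**

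- Sample Size: 49 evaluable patients per arm, two-sided alpha 0.05, 80% power, difference 4.1 − 2.4 = 1.7 mg, SD 3 mg.
- SD for this pair: 1.3 mg for Exparel (Sample Size) and 1.3 mg for the catheter (Rationale for this Study).
- SD 3 mg is the single-shot value and is reported for neither of these two arms. It serves here as a sensitivity case.
- Assumed by me, because the plan gives no margin: true excesses of opioid use on Exparel of 0.5 mg and 0.85 mg (half of 1.7 mg).

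**The plan's own figure.** n per arm = 2 × [SD × (1.96 + 0.8416) / difference]² = 2 × [3 × 2.8016 / 1.7]² = 48.9, so 49. This agrees with the plan. An exact t calculation gives 49.9, so 50. The figure concerns single shot versus Exparel.

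**Precision for catheter versus Exparel.** Half-width of the 95% CI = t(0.975, 96 df) × SD × √(2/49).

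- SD 1.3: standard error 0.263 mg, half-width 0.52 mg.
- SD 3: standard error 0.606 mg, half-width 1.20 mg.

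**Chance of a non-significant result when Exparel is truly worse.** This is 1 minus the power of the two-sided t-test, from the noncentral t distribution with 96 df and noncentrality (true excess)/(standard error).

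| True excess on Exparel | SD 1.3 mg | SD 3 mg |
|---|---|---|
| 0.5 mg | 53% | 87% |
| 0.85 mg | 11% | 72% |
| 1.7 mg (full planned effect) | under 0.001% | 21% |

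With all 53 recruited patients per arm analysed, the half-widths are 0.50 and 1.16 mg, and the first row becomes 50% and 86%.

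**What a real similarity claim would need.** Illustrative margin 0.85 mg, true difference zero, 95% CI, normal approximation:

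- Non-inferiority power at 49 per arm = Φ(0.85/SE − 1.96): 90% at SD 1.3, 29% at SD 3.
- Equivalence power at 49 per arm = max(0, 2Φ(0.85/SE − 1.96) − 1): 80% at SD 1.3. It is 0% at SD 3, where the half-width exceeds the margin.
- n per arm for 80% power, non-inferiority = 2 × [SD × (1.96 + 0.8416)/0.85]²: 37 at SD 1.3, 196 at SD 3.
- n per arm for 80% power, equivalence = 2 × [SD × (1.96 + 1.2816)/0.85]²: 50 at SD 1.3, 262 at SD 3.

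Whether 49 per arm could support the claim therefore depends on a margin that the plan does not set and on the SD.

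**The case against.** **The sentence is not a decision rule.** It calls the result beneficial, while the formal criterion is superiority. Catheter versus Exparel is neither the primary nor the named secondary comparison in the Statistical Analysis Plan. This stands and limits the weight of the point. It does not remove it, because similarity is also written into the Primary Hypothesis.

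**At SD 1.3 mg a non-significant result is informative.** The observed difference would be below 0.52 mg, so the 95% CI would lie within about ±1.04 mg (2 × 0.52) and exclude a loss of 1.7 mg. That is correct, but the information comes from the interval, which the plan does not commit to reporting. At SD 3 mg the bound widens to about ±2.41 mg and the reassurance disappears.

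**The SD is uncertain.** The documents give the same mean and SD for both techniques, and one pair may be carried over from the other. The values are also 48-hour figures, while the Analysis Plan speaks of 72 hours. This is fair, and it is why both SDs are shown.

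**The conflict may be milder than it looks.** The success criterion joins its two comparators with *or*, so beating Exparel may be only one route to success. The clash between the Primary Hypothesis and the Analysis Plan remains on any reading.

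**Conclusion.** The concern holds. The planned analysis cannot support the similarity conclusion that the success criteria attach to a no-difference finding. At SD 1.3 mg the practical risk is that modest losses are passed over: 53% for 0.5 mg and 11% for 0.85 mg, with virtually no chance of missing the full 1.7 mg. At SD 3 mg even the full effect would be missed 21% of the time. These figures assume 49 evaluable patients per arm, equal SDs and a t-test. The reasoning does not depend on them: without a margin, a non-significant p-value is not evidence of similarity at any sample size. The point should be corrected, but it does not threaten the comparisons with single-shot bupivacaine.

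**What to change.** Replace the no-difference sentence under Study success criteria with wording such as:

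> *The Exparel minus catheter difference in mean total opioid use over the primary time window will be reported with a two-sided 95% confidence interval, whichever test is used for the p-value. A non-significant result alone will not be taken as evidence of similarity.*

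Then:

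- Name the interval method in the Statistical Analysis Plan, for example Welch t. State how it will be read beside a Wilcoxon p-value, since the two can disagree.
- Reconcile the Analysis Plan and success criteria (catheter better than Exparel) with the Primary Hypothesis and section B (the two alike).
- Settle the primary window first. The Primary Aim uses 48 hours and the Analysis Plan 72.
- Preferably, make the Publication Plan speak of no *statistically significant* difference.

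The cost is a few sentences and one reported interval, with no added patients. The downside is that this comparison may end as inconclusive.

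If the sponsor wants a positive claim, a margin must be justified and fixed before any comparative data are seen, since the trial is open. Non-inferiority in opioid use then needs the upper confidence limit below the margin. Similarity needs both limits within plus or minus the margin. Either claim would concern opioid use; a claim about pain control would need its own rule for the pain scores. The intention-to-treat and per-protocol sets should be defined first, because Early Withdrawal of Subjects leaves open how failed catheter placements are analysed, and the result should hold in both sets. The sample sizes above use a 95% interval. Equivalence judged on a 90% interval would need 41 per arm at SD 1.3 mg or 214 at SD 3 mg for the same illustrative 0.85 mg margin.

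### Enrolling 53 per arm does not keep the required 49 after 10% dropout; under the plan's SD of 3, t-test power is about 78%, not 80% (minor)

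*Combined protocol and SAP*

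**What the plan says.** All the inputs are in Section G, Statistical Methods, Sample Size. The assumed opioid totals are "4.1 mg (SD 3 mg) in single shot group and 2.4 mg (SD 1.3 mg) in Exparel TAP group". For the calculation, "a standard deviation of 3 is used as a conservative estimate". The result is that "a sample size of 49 patients per arm is required to achieve 80% power with a significance level of 0.05", with the test described as "using a two-sided t-test or Wilcoxon rank-sum test depending on normality test". The enrolment figure follows: "Allowing for a 10% dropout rate, a total of 159 participants with 53 participants in each arm will therefore need to be recruited".

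Two other places bear on this:

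- The Statistical Analysis Plan in Section G sets the rule for choosing the test: "student's t-test if data are normal distributed or Wilcoxon rank-sum test if not normal distributed".
- Missing Outcome Data in Section G leaves missing values out of the analysis and says this might prompt further recruitment. Early Withdrawal of Subjects in Section E offers replacement as one of two options after a failed block. Neither gives a number or a trigger.

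**The concern.** The paragraph sets a requirement of 49 per arm and then an enrolment figure meant to protect it from 10% loss. The two do not fit together, because a 10% loss from 53 leaves fewer than 49. Since missing outcomes are excluded from the analysis, power depends on the evaluable number and not on the enrolled number.

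In addition, 49 comes from a formula that treats the SD as known, whereas the test named is a t-test. Both roundings go in the same direction, so the 80% quoted for the primary comparison is slightly too favourable on the plan's own inputs. What is at stake is the accuracy of that statement; the conduct of the trial does not depend on it.

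**Working it through.** **Inputs** (Section G, Sample Size): difference 4.1 - 2.4 = 1.7 mg; common SD 3 mg; two-sided alpha 0.05; target power 80%; equal arms; 53 enrolled per arm; 10% dropout.

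**1. Reproduce the 49.** By the normal approximation,

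n = 2 x SD² x (z0.975 + z0.80)² / difference² = 2 x 9 x (1.960 + 0.842)² / 1.7² = 48.9, rounded up to 49.

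Approximate power at 49 is 80.1%, so the plan's figure is reproduced by this formula.

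**2. Dropout allowance.**

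- Left after 10% loss: 53 x 0.9 = 47.7, against the 49 required.
- Enrolment that keeps 49: 49/0.9 = 54.4, so 55.
- Even the cruder inflation gives 49 x 1.1 = 53.9, so 54.
- Loss that 53 can absorb: (53 - 49)/53 = 7.5%.

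This step needs no assumption about the distribution of the outcome.

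**3. Exact t-test power.** Use the noncentral t distribution with 2n - 2 degrees of freedom and noncentrality 1.7 / (3 x √(2/n)). At n = 50, for example, this is 1.7 / (3 x 0.2) = 2.83.

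| Evaluable per arm | Normal approximation | Exact t-test |
|---|---|---|
| 47 | 78.4% | 77.6% |
| 47.7 | 79.0% | 78.2% |
| 48 | 79.3% | 78.5% |
| 49 | 80.1% | 79.3% |
| 50 | 80.9% | 80.1% |

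The t-test first reaches 80% at 50 per arm. Going from 80.1% to 78.2%, about 0.8 point comes from the approximation (80.1% to 79.3% at 49) and about 1.1 points from the dropout shortfall (79.3% to 78.2%).

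**4. Arm-specific SDs.** With SDs of 3 and 1.3, the approximate requirement is (3² + 1.3²) x (1.960 + 0.842)² / 1.7² = 29.0 per arm, so 30. Simulated power at 48 per arm with normal data is about 95% for the t-test and 93% for the Wilcoxon test.

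**5. Wilcoxon test.** For normal data with SD 3 in both arms, the relative efficiency of 3/π = 0.955 gives 75.6% at 47, 76.5% at 48 and 77.4% at 49, with 53 evaluable needed for 80%. For skewed data, simulated Wilcoxon power at 48 per arm was:

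| Assumed shape | SDs | Wilcoxon power |
|---|---|---|
| Gamma | 3 and 1.3 | 85% |
| Lognormal | 3 and 1.3 | 95% |
| Shifted gamma | 3 and 3 | 90% |
| Gamma | 3 and 3 | 97% |
| Lognormal | 3 and 3 | 99% |

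These shapes are assumptions; the documents give no distribution.

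**The case against.** The strongest reply is that 49 is a correct textbook answer. The standard formula gives it exactly, and the exact t-test differs by one patient per arm and 0.7 point of power. That is a choice of approximation and not a mistake, and on its own it would not deserve a comment. This stands for the 49, but it does not rescue the 53: neither usual way of inflating 49 for 10% loss, rounded up, gives 53.

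A second reply is that SD 3 in both arms is a declared safety margin. The Exparel arm's quoted SD is 1.3, and with the quoted pair power is far above 80%. This also stands, and it is why the point is minor. The 80% is nevertheless stated for SD 3, and under SD 3 it is not delivered.

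A third reply is that losses may be made good by extra recruitment or replacement. The wording permits this but does not require it, so it does not guarantee 49 evaluable patients.

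A reader might also infer that the Wilcoxon test delivers only about 76% after dropout and needs 53 evaluable per arm. A mean of 4.1 with SD 3 on a quantity that cannot be negative makes non-normality plausible, and with it the Wilcoxon test. The documents do not support that inference. The 76% holds for normal data, for which the plan uses the t-test. Once the data are skewed enough for the Wilcoxon test to be chosen, the 0.955 efficiency no longer applies, and every skewed case tried gave 85% or more at 48 per arm.

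**Conclusion.** The point holds as a minor correction. Enrolling 53 per arm with 10% loss leaves 47 to 48 evaluable, fewer than the 49 that the same paragraph requires. On the plan's inputs (difference 1.7 mg, SD 3 in both arms, two-sided 0.05, normal data), t-test power is then 77.6% to 78.5%, against the stated 80%. The shortfall is about 2 points.

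The size rests on losses reaching the full 10% without being made good, and on the conservative SD. The dropout mismatch itself rests on arithmetic alone.

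It would be wrong to conclude that the trial is underpowered: the quoted SDs of 3 and 1.3 point the other way. The Wilcoxon part of the power claim is neither confirmed nor refuted, because the plan names no distribution for it.

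**What to change.** Restate the figure in Section G, Sample Size, for example:

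> 53 enrolled per arm with 10% loss leaves 47 to 48 evaluable, giving about 78% power (t-test, SD 3 in both arms); power is higher under the quoted SDs of 3 and 1.3.

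For the Wilcoxon test, either state the distribution assumed for its power or limit the power statement to the t-test. Do not insert the 76% normal-data figure, since the plan would not use the Wilcoxon test on such data.

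The cost is one sentence and a slightly less favourable stated power. No enrolment change is required. If the sponsor prefers to keep the 80% claim under SD 3, the matching enrolment is 55 per arm (165 in total) to retain 49, or 50/0.9 = 55.6, so 56 per arm (168 in total), to retain the 50 that the exact t-test needs.

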Subjects may be withdrawn from the study early due to complications secondary to the surgery itself such as sepsis, bowel dysfunction unrelated to narcotic use, and the need for further exploratory surgery.

Catheter dysfunction due to dislodgment or severe leakage may also precipitate early withdrawal from the study. Bleeding, infection, or need to anti-coagulate may cause premature need to remove the catheters from the patients. In these cases, the data will continue to be recorded as in the other arms; however, time of catheter removal will also be recorded.

Failure to perform an adequate block will also cause withdrawal from the study. Reasons for said failure would include: inability to visualize TAP space on ultrasound and surgical site preventing use of bilateral TAP block.

Failure to place catheter after successful bolus of local anesthetic would move patients from the CTAP group to an un-randomized single shot Bupivacaine arm. Patients will be followed until completion of the study. This data may be analyzed separate or as part of the single shot Bupivacaine group.

Failed block is a withdrawal prior to first study follow up; these patients would need to be replaced or moved to an open un-randomized arm.

Subjects may also be withdrawn from the study if at any time it is determined that they did not meet inclusion exclusion criteria.

iii Subject safety

iv Non-compliance with study visit schedule or study regimen

Subjects may be involuntarily exited from the study for failure to comply with the protocol, failure to attend follow-up visits, or for other reasons. The investigator shall arrange for an exit visit and complete the case report form for the subject to the extent there is data available.

Subjects may voluntarily withdraw from the study at any time without reason. The investigator shall make an effort to obtain an exit visit and complete the case report form for the subject to the extent there is data available. The investigator cannot require that an exit interview take place.

E2.g Data Collection and Follow-up for Withdrawn Subjects

- 1) Reason for withdrawal from study (i.e. block failure, catheter failure, drug toxicity, sepsis, patient request)
- 2) Day of withdrawal from study

Study Drug/Device

E3.a Description

The ON-Q[®] device is considered a non-significant risk device which has been marketed for postoperative pain management since 1998.

Description of Device:

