All study sites will observe Health Insurance Portability and Accountability Act (HIPAA) Privacy and Security Rule standards.

Training

All research team members must complete approved Human Subjects and HIPAA training.

All research team members must complete Oncore ERM training.

Case Report Forms and Source Documents

Study sites will utilize the data collection forms in Attachment L9 to collect data and will enter data into the Oncore ERM study management system.

Records Retention

Paper study records will be maintained at the respective study sites for seven years from the end date of the study. At the end of this time period, study records will be shredded.

Data in the Oncore ERM study management system will be stored for seven years from the end date of the study. At the end of this time period, records will be deleted.

Performance Monitoring

The IRB and the Principal Investigator will monitor study performance using the Oncore ERM study management system.

I Study Monitoring, Auditing, and Inspecting

Study Monitoring Plan

The IRB and the Principal Investigator will monitor ongoing study performance using the Oncore ERM study management system.

Auditing and Inspecting

The IRB will audit and inspect study materials at the study sites as indicated.

J Study Administration

Organization and Participating Centers

The Principal Investigator at the lead institution will collaborate with study site Principal Investigators to oversee this study.

Funding Source and Conflicts of Interest

There are no conflicts of interest among any of the study investigators.

Study investigators must complete institution-specific conflict of interest forms as required.

Subject Stipends or Payments

Subjects will not be paid for their participation in the study.

Study Timetable

The study will last for approximately four months. This is the estimated time based on current operating room patient criteria to enroll ninety patients into the study.

κ Publication Plan

Upon completion of study and statistical methods, it would be expected to publish the study in an established and well-read peer journal of either Anesthesiology or Surgery. Given that an analysis demonstrating a statistically significant difference or no difference between any of the study arms would be useful to how anesthesiologist and/or the surgical team approach the TAP block, it is highly likely the study would be accepted for publication.

L Attachments – TAP Block Pain Management Data Form

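### The plan gives two enrolment totals, 159 and ninety, and its stated accrual of 8 per week does not lead to a duration of around one year

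*Combined protocol and SAP*

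**What the plan says.** The Sample Size section under Statistical Methods (section G) compares means of 4.1 mg and 2.4 mg. Although it reports SDs of 3 mg and 1.3 mg, it notes that "a standard deviation of 3 is used as a conservative estimate". On that basis "a sample size of 49 patients per arm is required to achieve 80% power with a significance level of 0.05". It continues "Allowing for a 10% dropout rate" and concludes that "a total of 159 participants with 53 participants in each arm will therefore need to be recruited into the study". On timing it says: "It anticipated that approximately 8 participants per week will be enrolled into this study, thus the estimated accrual time is around 1 year".

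The Study Timetable in section J says "The study will last for approximately four months" and explains: "This is the estimated time based on current operating room patient criteria to enroll ninety patients into the study".

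Two other places touch on final numbers. Early Withdrawal of Subjects says of failed blocks that "these patients would need to be replaced or moved to an open un-randomized arm". Missing Outcome Data allows for recruiting more patients into one or more arms. Neither gives a number.

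**The concern.** A reader finds two totals for the same trial. Nothing describes ninety as an interim, single-site or evaluable count, and nothing marks either figure as superseded. The Sample Size section presents one year as following from 8 per week, but that inference fails on simple division. The two sections also disagree on duration.

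The IRB and the Principal Investigator are to monitor study performance. With these figures they cannot tell whether recruitment is on schedule, late or complete. The more serious risk is that someone treats ninety as the point at which recruitment is finished, which would leave the main comparison with fewer patients than its calculation requires.

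**Working it through.** **Inputs.** From Sample Size: difference 4.1 − 2.4 = 1.7 mg; common SD 3 mg (reported SDs 3 and 1.3 mg); two-sided alpha 0.05; 80% power; 49 evaluable and 53 recruited per arm; 10% dropout; 8 patients per week; around one year. From Study Timetable: ninety patients; about four months. Conversions: one year = 52.2 weeks; four months = 17.4 weeks.

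**1. The plan's own sample size.** Normal approximation: n per arm = 2 × (1.96 + 0.8416)² × 3² / 1.7² = 48.9, so 49. This reproduces the plan. The exact t calculation gives 49.9, so 50; power at 49 is 79.3%. The 159 is 3 × 53. Ninety is not derived anywhere in the documents.

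**2. The totals.** 159 − 90 = 69 patients.

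**3. Accrual.**

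| Assumption | Calculation | Result |
|---|---|---|
| 159 at the stated 8 per week | 159 / 8 | 19.9 weeks, 4.6 months |
| 159 in one year | 159 / 52.2 | 3.0 per week |
| 8 per week for one year | 8 × 52.2 | about 417 patients |
| Ninety in four months | 90 / 17.4 | 5.2 per week |
| 159 at the timetable's implied rate | 159 / 5.17 | 30.7 weeks, 7.1 months |
| 159 in four months | 159 / 17.4 | 9.1 per week |

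One year is too long by 52.2 / 19.9 = 2.6 times at the stated rate. Reading the rate as 8 per month does not help: 159 / 8 = 19.9 months.

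**4. Power if ninety were used as the target** (difference 1.7 mg, two-sided 0.05).

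| Evaluable per arm | t-test, SD 3 in both arms | Welch t, SDs 3 and 1.3 |
|---|---|---|
| 30 (no loss) | 57.9% | 79.3% |
| 27 (10% loss) | 53.3% | 74.8% |

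**5. Dropout allowance.** 53 × 0.9 = 47.7, so 47 to 48 evaluable, below 49. The loss that 53 can absorb is 1 − 49/53 = 7.5%, or 4 patients per arm. Dividing correctly, 49 / 0.9 = 54.4, so 55 per arm and 3 × 55 = 165 in total. Multiplying instead, 49 × 1.10 = 53.9, which gives 53 only if truncated. The cost is small: power is 77.6% at 47 and 78.5% at 48, against 79.3% at 49 (SD 3). With SDs of 3 and 1.3 mg it stays near 94%.

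**The case against.** The strongest reply is that only Sample Size sets a target. Its figure is derived and worded as a requirement, whereas the Study Timetable is an administrative estimate of calendar time. No test, error rate or decision rule uses ninety, four months, 8 per week or one year. This stands, and it is why low power is a risk of leaving the text unreconciled and not a planned outcome.

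Second, the power loss depends on the SD. With the SDs the plan reports, 30 per arm gives about 79%, close to the 80% sought. The normal approximation with those SDs needs (1.96 + 0.8416)² × (9 + 1.69) / 1.7² = 29.03, so 30 per arm and 90 in total without dropout. That may be where ninety came from, but this is inference; the documents do not say so. The point stands as a reason to quote a range. It does not restore ninety, because the plan expressly adopts SD 3.

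Third, four months is not far off at 8 per week: 8 × 17.4 = 139 patients, and 159 would need about two and a half weeks more. This also stands. The clear duration error is pairing 8 per week with one year.

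Fourth, the dropout shortfall is minor, and replacement of failed blocks or extra recruitment may offset part of it. That is fair, though neither provision sets a number.

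**Conclusion.** The concern holds, and the plan is wrong as written on both counts. The totals differ by 69 patients, and the stated rate gives about 20 weeks where the plan concludes around one year. These results need only division and subtraction of the plan's own figures. The documents do not settle whether the rate or the duration is the mistaken one.

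The 49 per arm is sound, and 159 is the only total with a derivation behind it. The effect on power is conditional on ninety being used as the target. It would then be 58% to 79% before dropout and 53% to 75% after 10% loss, with the lower figures applying under the plan's SD of 3 mg and the upper under SDs of 3 and 1.3 mg. The dropout slip costs about 1 to 2 percentage points of power at SD 3. This should be fixed, but it does not undermine the design.

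**What to change.** - **Study Timetable (section J):** replace ninety with 159, and change the four-month duration to match the chosen rate.
- **Sample Size (section G) and Study Timetable:** state one accrual rate, chosen by the sponsor from what is known of recruitment, and the duration it gives for 159: about 20 weeks at 8 per week, about 7 months at 5 per week, or about one year at 3 per week.
- **Sample Size, dropout:** say either that 53 per arm keeps 49 evaluable with up to about 7.5% loss, or that 10% loss leaves about 48 evaluable per arm and about 78% power at SD 3. Only if the sponsor wants both 10% loss and 49 evaluable is a larger sample needed: 55 per arm, 165 in total, with section J changed to the same figure.

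The cost is wording in two sections. The optional increase adds 6 patients. If recruitment has in practice been set up around ninety, keeping to 159 means 69 more patients than the timetable assumed. Design and analysis stay as they are.
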